# 12.0 Risks to Participants

#### 12.1 Foreseeable Risks:

Risks of blood sampling: There is a minimal risk of bruising, fainting and infection associated with blood draws.

Risks of exposure to ionizing radiation: The DXA scans and the bone age scans involve exposure to a very low dose of ionizing radiation. The average amount of radiation that the average person would receive from the bone age scan and DXA scans used in this study is less than 2% (3 mrem) of that received from natural sources of radiation by a Minnesota resident in one year (300 mrem).

Risks of Lisdexamfetamine: Adverse reactions occurring in ≥5% and at a rate at least twice that of placebo in children include anxiety, dry mouth, diarrhea, nausea, vomiting, upper abdominal pain, irritability, insomnia and dizziness. Rarely reported adverse events include hypertension and tachycardia. Additionally, suppression of linear growth is a known class effect, though final adult height is not impacted.

Although not recommended as a routine practice, baseline ECG will be obtained on all participants to screen for underlying arrhythmia. If SBP and/or DBP is ≥95th percentile or ≥130/80 (whichever is lower), blood pressure will be measured again on a separate visit within 2 weeks. If BP remains elevated on 3 separate visits, the participant will undergo a 24 hour ambulatory blood pressure monitor (ABPM) to confirm or rule out a diagnosis of hypertension.

If elevated BP emerges and is confirmed on 2 additional occasions during lisdexamfetamine dose escalation, further dose escalation will halt until the results of a 24 hour ABPM are available.

If hypertension is confirmed, lisdexamfetamine dose will be reduced until blood pressure normalizes.

- If SBP and/or DBP is ≥95th percentile+12 mmHg or ≥140/90 (whichever is lower) and the participant is symptomatic, lisdexamfetamine will be discontinued and the participant will be referred to emergent care.
- If heart rate is ≥140 bpm, an EKG will be obtained and the participant will be assessed for the need for emergent or non-emergent medical intervention, including the need to reduce or discontinue lisdexamfetamine dose.

*Risks of indirect calorimetry*: Potential risks include feeling claustrophobic from the mask/hood.

PROTOCOL TITLE: Lisdexamfetamine for the Treatment of Severe Obesity in Children Aged 6 to 12 Years

VERSION DATE: 19Sep2025

*Risks of Accelerometry*: Potential risks include emotional distress from wearing the device 24 hours per day.

Risks of lifestyle therapy: Potential risks related to lifestyle therapy is sadness or frustration related to difficulty adhering to dietary and activity plans. Participants may experience injury related to increased physical activity. In our experience, participants tolerate lifestyle therapy without difficulty.

Risks of neuropsychological assessments and eating questionnaires: Potential risks include emotional distress and possible "test fatigue."

Risks of changes in mental health status: Individuals whose C-SSRS levels increase to a Moderate or High risk or whose CDI-2 values increase to a level of  $\geq$  70 (by either child or parent report) after the screening and baseline/randomization visits will have these values reported to a peds psychologist (either [name] or [name]) and they may be referred to their mental health professional (if one is pre-existing) or provided with names of a mental health professional if one is not already in place.

- 12.2 Reproduction Risks: Exposure to ionizing radiation may cause harm to an unborn fetus. Therefore, all females will have a pregnancy tests before they undergo the bone age x-ray or the DXA scan.
- 12.3 Risks to Others: Not applicable.

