#### 3.3 Description:

LDX: LDX, a psychostimulant prodrug of dextroamphetamine, is FDA-approved for ADHD in children ≥6 years of age and for binge eating disorder in adults. It is available in capsules of 10, 20, 30, 40, 50, 60, and 70 mg. It is orally administered once daily and has a half-life of 12 hours. After a single dose, the pharmacokinetics are linear between 30 and 70 mg in children ages 6-12 years, and both the clinical efficacy for ADHD symptoms and weight loss side effects are dose dependent. Following single doses of 30 mg to 70 mg, the weight/dose normalized area under the curve and maximal concentration values are the same in 6-12 year olds compared to adults. Per the package insert, the recommended starting dose for children ≥6 years of age with ADHD is 30 mg daily. The dose is adjusted by 10 or 20 mg increments at weekly intervals up to a maximum of 70 mg daily. The target dose is one that balances the clinical efficacy with tolerability. For binge eating disorder in adults, the recommended dose is 50-70 mg daily. To operate conservatively and allow for maximum tolerability, we will start at 30 mg daily for 2 weeks, then 40 mg daily for 2 weeks, then 50 mg daily for 2 weeks, then 60 mg daily for 2 weeks, then 70 mg daily for the remaining 14 weeks. We will not use a forced titration schedule. That is, for patients who do not tolerate the full dose escalation schedule, we will maintain the dose at the maximum tolerated dose for the remainder of the trial. Also, we will not escalate the dose after week 10, which is the end of the planned dose escalation schedule. A participant's dose may be decreased for medication intolerance anytime during the trial; the dose will be reduced by 10 mg at weekly intervals until a tolerable dose is achieved. If a participant cannot tolerate the smallest dose, 10 mg, then drug/placebo will be discontinued but the participant will remain in the trial. This flexible dosing will allow for maximal time on medication. Placebo capsules that are identical in appearance to the LDX capsules will be made by the University of Minnesota Investigational Drug Service Pharmacy, which will manage all trial product.

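### Section 12.1 requires no dose hold or clinical assessment for a child without symptoms whose blood pressure is at or above the 95th percentile + 12 mmHg or 140/90

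*Combined protocol and SAP*

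**What the plan says.** Section 12.1 works with two blood-pressure levels.

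- **Lower level** (95th percentile or 130/80, whichever is lower). After one elevated reading, "blood pressure will be measured again on a separate visit within 2 weeks". "If BP remains elevated on 3 separate visits", 24-hour ambulatory monitoring (ABPM) follows. The dose-related rule is: "If elevated BP emerges and is confirmed on 2 additional occasions during lisdexamfetamine dose escalation, further dose escalation will halt", pending the ABPM result. If hypertension is confirmed, the dose comes down.
- **Upper level** (95th percentile + 12 mmHg or 140/90, whichever is lower). The one specific action is conditional: "and the participant is symptomatic, lisdexamfetamine will be discontinued", with emergent referral.

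The heart-rate bullet that follows is built differently. A rate of 140 bpm or more leads to an EKG and an assessment, "including the need to reduce or discontinue lisdexamfetamine dose". It needs neither symptoms nor a second reading.

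Section 3.3 sets the titration from 30 to 70 mg in 10 mg steps every two weeks. It adds "We will not use a forced titration schedule" and "we will not escalate the dose after week 10, which is the end of the planned dose escalation schedule". The schedule of events in Section 4.1 puts the increases at Weeks 2, 4, 6 and 8. During titration, on-drug blood pressure is scheduled only at Weeks 4 and 8. The visit lists under Section 7.3 for those two weeks include both the measurement and a dose step, the latter subject to tolerance.

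**The concern.** The upper level is one at which the plan would stop the drug and send a child with symptoms to emergent care. For a child with the same reading and no symptoms, Section 12.1 gives nothing beyond what it gives a child just over the 95th percentile. Nothing in it addresses the increase planned for that same visit.

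The background in Section 2.1 describes the blood-pressure effect of psychostimulants as tending to be dose dependent in children with ADHD. It calls the clinical significance uncertain, especially in children with obesity. Raising the dose at such a reading, before any recheck, is avoidable exposure in children aged 6 to under 12. It also leaves the decision to individual judgement in a trial where the incidence of hypertension is one of the feasibility criteria (Section 14.0, Aim 2).

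**Working it through.** The plan states no figure here to reproduce. The check sets the rules side by side and then follows the calendar.

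**What one reading triggers under Section 12.1**

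| Single reading | Symptoms needed? | Required action |
|---|---|---|
| BP at lower level | No | Recheck within 2 weeks; no hold |
| BP at upper level, with symptoms | Yes | Stop drug, emergent referral |
| BP at upper level, no symptoms | – | No specific rule; lower-level pathway only |
| Heart rate ≥140 bpm | No | EKG and assessment, including dose |

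**Inputs for the calendar**

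- Dose steps (Section 3.3; schedule of events): Week 2 to 40 mg, Week 4 to 50, Week 6 to 60, Week 8 to 70.
- Visit windows through Week 10: ±3 days (schedule of events).
- First recheck: within 14 days. The next recheck has no stated interval; I assume 1 to 14 days.
- Further assumptions: blood pressure is read before that day's dose decision, the scheduled Week 8 reading counts towards the three, every reading is elevated, and an occasion means a separate visit.

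**Upper-level reading without symptoms at Week 4.** The child is on 40 mg.

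1. The step to 50 mg is allowed the same day: 50 − 40 = +10 mg.
2. The gap from the Week 4 to the Week 6 visit is (42 ± 3) − (28 ± 3) = 8 to 20 days. A first recheck that is on time at 14 days can therefore fall after the Week 6 step.
3. If both rechecks are done before the Week 6 step, the halt stops Weeks 6 and 8. Total before the halt: +10 mg.
4. Otherwise the Week 6 step is also given: 60 − 40 = +20 mg. The halt then stops only Week 8, at the latest on the scheduled Week 8 reading.

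**Upper-level reading without symptoms at Week 8.** The child is on 60 mg. The step to 70 mg is allowed the same day: 70 − 60 = +10 mg. No planned step remains for the halt to stop.

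A day-by-day enumeration, with and without the windows, gave only these outcomes: one step before the halt and two stopped, or two before and one stopped (Week 4 onset); one before and none stopped (Week 8 onset).

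**With a mandatory hold at the upper level,** the increase following that reading is +0 mg while the hold lasts. The price in final dose, compared with the current text:

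| Path | Current text | With hold |
|---|---|---|
| Week 4 reading, below the level by Week 6, held step made up at Week 10 | 70 mg | 70 mg, later steps 2 weeks late |
| Same, but Week 10 not used | 70 mg | 60 mg |
| Week 8 reading, cleared only after Week 10 | 70 mg | 60 mg |
| At this level at Week 4, first recheck and Week 8; ABPM clear after Week 10 | 60 mg | 40 mg |

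The documents give no rate of readings at the upper level, so I give no expected number of children.

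**The case against.** **Discretion already covers it.** Titration is not forced, each step depends on tolerance, study physicians write the prescriptions (Section 3.4), and the dose may be cut at any time for intolerance. A careful physician would not raise the dose at such a reading. This stands to the extent that the plan permits an increase and does not direct one. It does not supply a rule. Under Section 4.2 the parent and child judge whether side effects are bad enough to stop the drug or go below 30 mg, and they may not notice a rise without symptoms. Hypertension appears there as a tolerability measure only after three occasions and ABPM.

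**The child is not left without follow-up.** A reader might infer that nothing happens. That is wrong: the recheck, ABPM after three elevated visits, and dose reduction on confirmed hypertension all apply, including after Week 8. Children meeting the three-occasion definition at entry are excluded (Section 7.2).

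**The harm is small.** The extra dose is 10 to 20 mg. On the package insert, Section 3.3 reports: "The dose is adjusted by 10 or 20 mg increments at weekly intervals up to a maximum of 70 mg daily". This trial steps more slowly. Section 2.1 cites mean systolic rises of 2 to 4 mmHg in ADHD trials and gives no effect per 10 mg. With 1:1 allocation, about half of any held children would be on placebo. All of this stands and limits the weight of the point.

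**'Occasions' is ambiguous.** Section 7.2 could be read as three readings within one visit. If the halt rule were read that way, it could act the same day, at +0 mg. That would need three elevated readings at one visit, and it still would not supply the missing assessment.

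**A stronger reading is tempting:** that the three-reading halt is itself wrong and any single reading at the lower level should stop escalation. The step counts above describe that halt correctly, but the documents do not support the inference. Three readings is the plan's consistent standard (Sections 4.2, 7.2, 12.1 and 14.0), and one-off readings are noisy. A hold at the lower level could leave a child whom ABPM later clears 10 to 30 mg below 70 mg, probably more often on lisdexamfetamine. Section 3.3 describes the weight effect as dose dependent, and the trial's purpose is to estimate the treatment effect. That change is an optional trade-off and is not recommended here.

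**Conclusion.** The gap is real and narrow. For a child without symptoms at or above the 95th percentile + 12 mmHg or 140/90, Section 12.1 requires neither a hold on escalation nor a clinical assessment, and at Week 4 or Week 8 the dose may go up at that same visit. Before the existing halt acts, the extra dose is 10 or 20 mg after a Week 4 reading and 10 mg after a Week 8 reading. Those counts assume that occasions are separate visits, that the first recheck is on time, and that no step is withheld at a physician's discretion. The absence of an assessment rule depends on none of these, and the plan gives no reason for treating blood pressure differently from heart rate. The harm cannot be put in mmHg or in events from the documents, and the frequency is unknown. This is a cheap safety improvement; it does not make the design unsound.

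**What to change.** After the bullet on symptomatic blood pressure in Section 12.1, add:

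*If BP is at this level without symptoms, study medication is not increased until a recheck is below this level or, if BP is elevated on 3 separate visits, until the ABPM result is available. The participant is also assessed to decide whether emergent or non-emergent care is needed and whether study medication should be reduced or stopped.*

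The second sentence follows the heart-rate bullet, without its EKG. Once a recheck is below the upper level, the existing lower-level pathway takes over. Thresholds, rechecks, ABPM, the three-reading halt and the Week 10 cap stay as they are.

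**Cost.** One clinical assessment per such reading; no blood-pressure recheck or ABPM beyond those Section 12.1 already requires. A held step may come late or be lost. Section 3.3 bars increases only after Week 10, but the Week 10 visit is virtual and lists no step. Making up a held 70 mg step then would need the capsules dispensed at Week 8 or at the recheck visit. The rule applies to both arms, so it does not reveal allocation.

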#### 13.0 Potential Benefits to Participants

13.1 Potential Benefits: Participation in the study will be restricted to children ages 6 to <12 years who have severe obesity and have a parent report of failing to lose weight with lifestyle therapy. Participants may benefit from participation in this study through close contact with the study staff and counseling on diet and physical activity which may result in weight loss. Participants randomized to active treatment will have access to experimental intensified treatment, lisdexamfetamine, which has been shown to cause weight loss in children treated for ADHD. The side effect profile of lisdexamfetamine is acceptable and the proposed study tests are not more than minimal risk.

#### 14.0 Statistical Considerations

Data Analysis Plan: Descriptive analyses of baseline characteristics and outcomes will include means and standard deviations, median and range for continuous variables and frequencies with percentages for categorical variables. Safety analyses (including Barkley's Side Effect Rating Scale and incidence of hypertension and tachycardia) will be primarily descriptive reporting the number and percentage of adverse events during participation in the study. All safety outcomes will be evaluated and monitored throughout the study. Confidence intervals (Cis) and P-values for all analyses will be based on robust variance estimation. Statistical significance will be considered as p<0.05.

PROTOCOL TITLE: Lisdexamfetamine for the Treatment of Severe Obesity in Children Aged

6 to 12 Years

VERSION DATE: 19Sep2025

**Aim 1:** Estimate the treatment effect of LDX plus lifestyle therapy vs placebo plus lifestyle therapy on changes in BMI (%BMIp95 primary endpoint), body fat, cardiometabolic health and quality of life (QOL) from baseline to 24 weeks. **H1:** We hypothesize that LDX compared to placebo will result in a greater mean decrease in %BMIp95 and body fat, and improved cardiometabolic health and QOL at 24 weeks.

The primary outcome measurement will be absolute change in percent of the BMI 95th percentile abbreviated %BMIp95. Although we will report on other metrics of BMI change including absolute BMI change and percent BMI change, we chose %BMIp95 as the primary outcome measurement because of its clinical utility in measuring changes in BMI in young children who have severe obesity and a consensus in the research community that expressing BMI change relative to the 95th percentile is preferred over other metrics such as BMI standard deviation score a.k.a. z-score. The limitation of BMIz is explained by the flattening of BMIz curve at values significantly above the 95th percentile, despite the wide variance of BMIs in youth with severe obesity, which therefore leads to an underestimation of clinically significant improvement in weight status). The primary outcome will be the mean change in %BMIp95 from baseline to 24 weeks follow-up compared between treatment groups, while adjusting for baseline value for added precision. See Table 1 for examples of changes in BMI and corresponding changes in %BMIp95.

| Table 1. Exa           | imples of chan             | ges in BMI and co                   | rresponding o            | changes in %BMIp                    | 95                                   |                                  |
|------------------------|----------------------------|-------------------------------------|--------------------------|-------------------------------------|--------------------------------------|----------------------------------|
| Example
Participant | Starting
BMI
(kg/m²) | Starting
%BMIp95                 | Ending
BMI
(kg/m2) | Ending
%BMIp95                   | Absolute
change in
BMI (kg/m2) | Absolute
change in
%BMIp95 |
| 6 yo girl              | 26.37                      | 140% of 95 th percentile | 25.2                     | 134% of 95 th percentile | -1.17                                | -6 percentage points             |
| 10 yo boy              | 39.8                       | 135% of 95 th percentile | 28.7                     | 130% of 95 th percentile | -1.1                                 | -5 percentage points             |

Power Analysis: Given this is a pilot and feasibility study, the sample size is not driven by a power analysis stemming from a formal statistical evaluation of a hypothesis test associated with the primary endpoint the trial. Instead, the objectives of this study revolve around identifying key information on execution of the study and experience of participants to best inform the design of a subsequent, larger study to examine efficacy and effectiveness.

Secondary endpoints for Aim 1 are also continuous and will be evaluated in a similar fashion, with adjustment for baseline value. These include percent body fat, lab measurements of glucose, insulin, lipids (total-, LDL-, HDL-cholesterol, and

PROTOCOL TITLE: Lisdexamfetamine for the Treatment of Severe Obesity in Children Aged

6 to 12 Years

VERSION DATE: 19Sep2025

triglycerides), hemoglobin A1c, ALT, AST, and PedsQL. We will also report on other metrics of BMI change, including absolute BMI change and percent BMI change.

**Aim 2:** Generate estimates of the tolerability and safety of LDX used for the treatment of severe obesity in children.

**H2:** We hypothesize that at least 80% of participants will tolerate an LDX dose of ≥30 mg daily (recommended starting dose) for 24 weeks and that the LDX group compared to the placebo group will not demonstrate clinically significant increases in blood pressure or heart rate.

We will define feasibility to conduct the larger trial if, in this pilot study, >80% of participants randomized to LDX tolerate a dose of >30 mg daily, the recommended starting dose, for 24 weeks and there are no statistically significant differences between the LDX group and placebo group in incidence of developing stage 1 hypertension or tachycardia. Outcomes will be captured for all regardless of tolerability and will inform inclusions/exclusion criteria and dose escalation schedule for the subsequent trial. Safety outcomes will be monitored carefully and include instances of stage 1 hypertension (defined as SBP and/or DBP ≥95th percentile on 3 separate occasions) and confirmed by 24 hour ambulatory blood pressure monitor) and tachycardia (defined as heart rate ≥120 bpm at rest measured on 3 separate occasions). The Barkley Side Effect Rating Scale will also be measured at every 2 weeks during dose escalation and then every 4 weeks for the remainder of the study and will be used to help identify reasons for limited tolerability should this occur. Height velocity in cm/year will be determined by the difference in measured height between the baseline and 24-week assessments and will be used to calculate a height velocity SDS (z-score). Given the potential for LDX to disrupt sleep and the impact of sleep on obesity, participant sleep will be measured objectively using accelerometry with the ActiGraph (GT3X-BT) device, which has been shown to have acceptable reliability and validity in sleep-wake detection compared with laboratory-based polysomnography. Nighttime sleep efficiency, defined as the portion of time dedicated to sleep that is spent asleep, will be evaluated as the primary sleep endpoint of interest, with higher scores representing more efficient sleep. All indexes will be calculated using the ActiLife software. Participant mental health will be monitored by the Columbia-Suicide Severity Rating Scale (C-SSRS) and Children's Depressive Inventory-2 (CDI-2).

**Exploratory Aim:** Examine potential mechanisms by which LDX reduces BMI in children with obesity. To do this, we will examine the effect of LDX on executive functioning skills, reward, appetite, resting energy expenditure and health behaviors (diet, eating behaviors, and physical activity). We expect that over the

PROTOCOL TITLE: Lisdexamfetamine for the Treatment of Severe Obesity in Children Aged 6 to 12 Years

VERSION DATE: 19Sep2025

24-week intervention, LDX compared to placebo will be associated with greater gains in executive functioning (measured by BRIEF-2 and NIH Toolbox), reduced reward responsiveness (measured by BIS/BAS), and reduced appetite (measured by visual analogue scale), which in turn will lead to more BMI reduction. Further, LDX compared to placebo will be associated with increased resting expenditure (measured by indirect calorimetry), leading to greater BMI reduction. Finally, we hypothesize that LDX compared to the placebo will be associated with greater reduction in calorie intake (measured by NDSR), binge eating (measured by (measured by CBES) and reward-based eating (measured by CEBQ), and a greater increase in physical activity (measured by accelerometry).

The exploratory evaluation of associations between treatment groups and exploratory endpoints will follow the same approach as in Aim 1 looking at mean differences in change from baseline. All endpoints are continuous and will have baseline measurements which will be used for baseline value adjustment for added precision in estimating contrasts between treatment groups and use robust variance estimation for the confidence interval and P-value. The results of these analyses will inform the larger definitive study in which these mediating relationships could be further defined.

14.1 Data Integrity: Impacting all aims, despite best efforts, it is possible that some data will be missing, which could limit the interpretation and generalizability of results. If the data are missing at random, conditioned on measured covariates, then supplementary analyses adjusting for these covariates will produce unbiased results. For potential missing data mechanisms beyond measured covariates, we will examine the extent to which results may be affected. Imputation techniques will be considered for missing data issues (e.g., multiple imputation). In particular, we will incorporate multivariate imputation by chained equations to handle missing data in follow-up visits. The imputation models will include baseline values and change from baseline. Additional variables for inclusion in the model include age, race, sex, Tanner stage, BMI, and LDX dose. We will also examine results without imputed values. If the analyses with and without multiple imputed values differ substantially, then exploratory analyses will be performed to evaluated factors that may have contributed to the differences.

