# 1.0 Objectives

1.1 Purpose: This will be a single site, 24-week double-blind, randomized, placebocontrolled pilot and feasibility clinical trial designed to estimate the treatment effect and tolerability of lisdexamfetamine (Vyvanse™) for the treatment of severe obesity in children ages 6 to < 12 years. After careful screening, all eligible participants (n=44) will be randomized, 1:1, to either lisdexamfetamine plus lifestyle therapy or placebo plus lifestyle therapy for 24 weeks of intervention. Participants and their parent/guardian will attend 8 in-person and 6 virtual visits. Participants will undergo regular assessments of anthropometrics, blood pressure, heart rate, and side effects and interval assessments of body composition, bone age, Tanner stage, laboratory tests, and questionnaires.

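### The all-analyses robust-variance rule does not suit the sparse hypertension and tachycardia comparisons: with no link named, the feasibility decision can turn on an unstated model choice

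*Combined protocol and SAP*

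**What the plan says.** The Data Analysis Plan in Section 14.0 sets one inferential rule: "Confidence intervals (Cis) and P-values for all analyses will be based on robust variance estimation". It adds that "Statistical significance will be considered as p<0.05".

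Under Aim 2 in the same section, one of the two conditions for calling the larger trial feasible is that "there are no statistically significant differences between the LDX group and placebo group in incidence of developing stage 1 hypertension or tachycardia". The other is that more than 80% of the LDX group tolerate the stated dose.

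Section 14.0 also says that safety analyses, naming the incidence of hypertension and tachycardia, "will be primarily descriptive reporting the number and percentage of adverse events during participation in the study". A comparative model is described only for continuous outcomes: change in %BMIp95 adjusted for baseline, then "Secondary endpoints for Aim 1 are also continuous and will be evaluated in a similar fashion, with adjustment for baseline value", and the same approach for the exploratory endpoints. For the two incidence comparisons the plan names no test, no link function and no rule for an arm without events.

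On size, Section 1.0 says "all eligible participants (n=44) will be randomized, 1:1, to either lisdexamfetamine plus lifestyle therapy or placebo plus lifestyle therapy", so about 22 per arm. On frequency, Section 12.1 says "Rarely reported adverse events include hypertension and tachycardia" and gives no rate.

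**The concern.** Robust (sandwich) variance is a reasonable default for baseline-adjusted mean changes. It fails for a log or logit model when one arm has no events. The estimated contrast then runs off towards infinity, while the sandwich standard error stays near 1. The Wald p-value falls below 0.05 whatever the number of events in the other arm. A model-based standard error grows with the estimate, so it gives no such signal.

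An arm without events is a realistic prospect. Section 12.1 calls both outcomes rarely reported. Section 7.2 excludes children who already meet hypertension or tachycardia criteria on three occasions. The Aim 2 definitions require three separate occasions and, for hypertension, ambulatory confirmation.

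At stake is the pilot's own feasibility condition. Describing the safety analyses as mainly descriptive does not remove the need for a p-value, because the condition is worded in terms of statistical significance.

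**Working it through.** **Inputs.** 44 randomized 1:1, taken as 22 per arm (Section 1.0). Threshold p<0.05 (Section 14.0), taken as two-sided because the rule refers to differences. Incidence is not given, so 1% to 15% in both arms is assumed. The plan states no figure for this comparison, so there is none to reproduce.

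**1. Robust logit at 1 vs 0.**
- Arm with one event: log-odds ln(1/21) = -3.04; sandwich variance 1/(22 × 1/22 × 21/22) = 22/21 = 1.048.
- Arm with no events, fitted risk e: each residual is -e, so the sandwich variance is 22e²/[22e(1-e)]², which tends to 1/22 = 0.045 as e falls to 0. The model-based variance, 1/[22e(1-e)], tends to infinity.
- SE of the contrast: at most about √(1.048 + 0.045) = 1.05. Software fits gave 1.02.
- p<0.05 needs a contrast above 1.96 × 1.05 = 2.05. That is reached once the fitted log-odds in the empty arm drops below -3.04 - 2.05 = -5.09, a fitted risk of about 0.6%. The fitting routine goes far past that point: the contrast stopped at about 20.

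The p-value printed depends on where the routine stops and means only that the result is spuriously below 0.05. Log-binomial and Poisson-log fits behave the same way (SE about 0.98). With model-based standard errors the same fits give p=0.999. Reversing the arms (0 on LDX, 1 on placebo) is also called significant. With no empty arm the artefact goes away: 2 vs 1 gives p=0.56.

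**2. Robust risk difference (identity link) and Fisher's test.** For x vs 0, the difference is x/22 and SE = √[(x/22)(1 - x/22)/22].
- 1 vs 0: 0.0455/0.0444 = 1.02, p=0.31.
- 4 vs 0: 0.1818/0.0822 = 2.21, p=0.027.
- Fisher at 4 vs 0: 2 × C(22,4)/C(44,4) = 2 × 7,315/135,751 = 0.108.
- Fisher at 5 vs 0: 2 × C(22,5)/C(44,5) = 2 × 26,334/1,086,008 = 0.0485.

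| Events | Robust log or logit | Robust risk difference | Fisher |
|---|---|---|---|
| 1 vs 0 | spuriously <0.05 | 0.31 | 1.00 |
| 2 vs 0 | spuriously <0.05 | 0.14 | 0.49 |
| 3 vs 0 | spuriously <0.05 | 0.062 | 0.23 |
| 4 vs 0 | spuriously <0.05 | 0.027 | 0.108 |
| 5 vs 0 | spuriously <0.05 | 0.011 | 0.0485 |

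**3. How often, with no true difference.** Let q = (1-p)^22 be the chance that an arm has no events. The chance that exactly one arm is empty is 2q(1-q). The error rate is the sum of the products of the two binomial probabilities over all tables with p<0.05.

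| Assumed incidence | q | 2q(1-q) | Error, robust logit | Error, robust risk difference | Error, Fisher |
|---|---|---|---|---|---|
| 1% | 0.802 | 32% | 32% | <0.1% | <0.1% |
| 2% | 0.641 | 46% | 46% | 0.1% | <0.1% |
| 5% | 0.324 | 44% | 44% | 1.5% | 0.3% |
| 10% | 0.098 | 18% | 18% | 4.3% | 1.4% |
| 15% | 0.028 | 5% | 7% | 5.2% | 2.2% |

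At incidences up to 10% nearly all the logit error comes from the empty-arm tables. Half of those have the excess on LDX (16%, 23%, 22% and 9% at 1%, 2%, 5% and 10%). The other half have it on placebo, which also breaches the rule as worded.

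**The case against.** The strongest reply is that the plan never calls for a log or logit model. Its only comparative model is a difference in means. Carried over to incidence, that is a robust risk difference, which obeys the sentence in full, gives p=0.31 at 1 vs 0 and needs one event fewer than Fisher to reach significance. This stands. A reader might infer that the plan prescribes a method that must declare a single case significant, or that a safe drug would be declared infeasible on one case. The documents do not support that: such a failure is possible under the sentence, not required by it.

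Three further points have weight. An alert statistician would probably notice an infinite odds ratio, and some fitting routines warn of non-convergence. The trial is a pilot in which "the sample size is not driven by a power analysis stemming from a formal statistical evaluation of a hypothesis test", and Section 17.2 provides an independent DSMB with a biostatistician. The error rates depend on an assumed incidence and fall to about 7% at 15%.

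None of this closes the gap. Baseline-adjusted mean change has no direct counterpart for a new-onset yes/no outcome, so the risk difference is an inference, not the plan's text. Replacing the test after an odd result has appeared, on a feasibility criterion, is what prespecification should prevent.

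A reader might also infer that the robust rule spoils the tolerability condition, because a Wald interval at 22/22 runs from 100% to 100%. It does not: that condition is stated as an observed proportion above 80%, and no interval enters it.

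**Conclusion.** The point holds in a limited form. A rule that puts every p-value and interval on robust variance is unsuitable for sparse binary outcomes, and the feasibility condition depends on two of them. Because no link is named, identical data such as 1 vs 0 can pass (risk difference, p=0.31) or fail (log or logit, spuriously below 0.05), and both analyses comply with Section 14.0.

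Under the log or logit choice, the false-positive rate per outcome is about 32%, 46%, 44%, 18% and 7% at true incidences of 1%, 2%, 5%, 10% and 15%. Under the risk difference it is near or below 5% throughout. These figures assume 22 evaluable children per arm, equal incidence in both arms and a two-sided test. The artefact arises only when exactly one arm has no events.

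This is a correction to make before unblinding. It does not invalidate the trial, and it does not affect the continuous endpoints.

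**What to change.** In Section 14.0:
- Limit the robust-variance sentence to the continuous endpoints.
- For the hypertension and tachycardia comparisons, prespecify one two-sided exact or score method, for example Fisher's or Barnard's test, with a Miettinen-Nurminen or exact confidence interval for the risk difference. Name a single test, since candidates can disagree near the threshold.
- As a minor reporting point, give the tolerability proportion a Clopper-Pearson or Wilson interval. At 22/22 the Clopper-Pearson lower limit is 0.025^(1/22) = 84.6%. This does not change the decision on the 80% criterion.

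The cost is one or two sentences, with no change to sample size, visits or consent. The downside is that exact tests are somewhat conservative: Fisher's first rejects at 5 vs 0, where the robust risk difference rejects at 4 vs 0. Because the condition is met when the test is not significant, a conservative test makes it easier to meet. Counts and the interval should therefore be reported beside the p-value.
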